9.7.3 Visit 1b

Visit 1b will be conducted in subjects who are administered study drug within 36 to 48 hours prior to cardiac surgery. The following procedures will be performed:

- Record concomitant medications.
- Obtain blood samples for blood biomarker testing.
- Obtain urine sample for urinary biomarker testing.
- Solicit any adverse events.

9.7.4 Visit 2 (Day 1)

9.7.4.1 Prior to Cardiac Surgery

The following procedures will be performed prior to the scheduled cardiac surgery on Day 1:

- Record changes in concomitant medications.
- Perform physical examination.
- Record vital signs.
- Obtain blood samples for serum chemistry, hematology, and blood biomarker testing.
- Obtain urine sample for urinary biomarker testing.
- Solicit any adverse events.

9.7.4.2 Post-Cardiac Surgery

The following procedures will be performed post-cardiac surgery on Day 1:

- Record changes in concomitant medications.
- Measure urine output.
- Solicit any adverse events.

9.7.5 Visits 3 – 8 (Days 2 – 7) or Discharge, If Earlier

The following procedures will be performed daily on Days 2 – 7 or discharge, if earlier, from the hospital:

- Record changes in concomitant medications.
- Perform physical examination; on Days 2 – 6, physical examination can be symptom-directed.
- Record vital signs.

- Obtain blood samples for serum chemistry and hematology.
- Measure urine output (Days 2 and 3 only).
- Obtain blood samples for blood biomarker testing (Days 2 and 3 only).
- Obtain urine sample for urinary biomarker testing (Days 2 and 3 only).
- Solicit any adverse events.

Note that the Day 7 visit may be conducted remotely as a virtual visit if an in-person visit is not possible. If a virtual visit is conducted: 1) blood and urine samples may be collected by remote phlebotomy, such as through a mobile phlebotomist or other blood collection center, and 2) the physical examination can be symptom-directed.

9.7.6 Visit 9 (Day 30)

Subjects will return to the site on Day 30 for the following procedures:

- Record changes in concomitant medications.
- Perform physical examination.
- Record vital signs.
- Obtain blood samples for serum chemistry and hematology.
- Obtain urine sample for urinalysis.
- Obtain urine sample for pregnancy testing in female subjects of childbearing potential.
- Solicit any adverse events.

Note that the Day 30 visit may be conducted remotely as a virtual visit if an in-person visit is not possible. If a virtual visit is conducted: 1) blood and urine samples may be collected by remote phlebotomy, such as through a mobile phlebotomist or other blood collection center, and 2) the physical examination can be symptom-directed.

9.7.7 Visit 10 (Day 60)

Subjects will return to the site on Day 60 for the following procedures:

- Record changes in concomitant medications.
- Record vital signs.
- Obtain blood samples for serum chemistry and hematology.
- Solicit any adverse events.

Note that the Day 60 visit may be conducted remotely as a virtual visit if an in-person visit is not possible. If a virtual visit is conducted, blood and urine samples may be collected by remote phlebotomy, such as through a mobile phlebotomist or other blood collection center.

9.7.8 Visit 11 (Day 90)/Final Visit

Subjects will return to the site on Day 90 for the following procedures:

- Record changes in concomitant medications.
- Perform physical examination, including weight and body mass index.
- Record vital signs.
- Obtain blood samples for serum chemistry and hematology.
- Obtain urine sample for urinalysis.
- Solicit any adverse events.

Note that the Day 90 visit may be conducted remotely as a virtual visit if an in-person visit is not possible. If a virtual visit is conducted: 1) blood and urine samples may be collected by remote phlebotomy, such as through a mobile phlebotomist or other blood collection center, and 2) the physical examination can be symptom-directed.

9.8 Clinical Laboratory Evaluations

Screening laboratory samples will be processed at a local laboratory. All other laboratory samples will be processed at a central laboratory. Each of the laboratory parameters to be evaluated during the study and collection times including serum chemistry, hematology, urinalysis, pregnancy testing, and biomarkers are detailed in the Event Schedule (see [Section 5](#)). Cystatin C will only be measured at Baseline (Visit 1a) and on Days 30 (Visit 9) and 90 (Visit 11).

Routine labs (serum chemistry, hematology, urinalysis) performed as part of standard of care within 1 month of dosing administration (Visit 1a) can be used for Screening assessments.

Blood and urine samples may be collected by remote phlebotomy, such as through a mobile phlebotomist or other blood collection center, for a visit conducted virtually on Day 7, 30, 60, or 90. Detailed instructions regarding sample collection and processing are provided in the laboratory manual.

9.9 Clinical Procedures and Observations

Investigators/study staff will regularly monitor subjects throughout study participation. At each post-cardiac surgery visit, the Investigator/study staff will record whether or not the subject is in the ICU, on a ventilator, has been discharged from the hospital, or readmitted to the hospital.

9.9.1 Medical History

A complete medical history will be obtained at Screening.

9.9.2 Concomitant Medications

All concomitant medications taken by the subject from the time of Screening through Day 90 will be recorded.

Concomitant medications that can cause photosensitivity should be avoided, if possible, during the study.

9.9.3 Physical Examination

Physical examinations will be performed by the Investigator or designee whose license permits the performing of physical examinations at the timepoints defined in the Event Schedule (see [Section 5](#)). Physical examinations should be performed at Screening, prior to dosing, prior to cardiac surgery on Day 1, Day 7, Day 30, and Day 90.

Physical examinations performed as part of standard of care within 1 month of dosing administration (Visit 1a) can be used for Screening assessments.

Symptom-directed physical examinations may be performed on Days 2 – 6. Symptom-directed physical examinations may also be performed on Days 7, 30, and 90 if those visits are conducted virtually.

Weight and body mass index will be collected at Screening and on Day 90.

9.9.4 Vital Signs

Vital signs (blood pressure, pulse rate, body temperature) will be collected throughout the study at the timepoints defined in the Event Schedule (see [Section 5](#)). During hospitalization, vital signs will be recorded once per day.

10 ADVERSE EVENT REPORTING

All adverse events will be recorded on the designated study eCRF for each subject beginning with the first administration of investigational product and ending with the date of the end of study treatment follow-up (Day 90). Adverse events will be followed by the Investigator until event resolution, the subject is lost to follow-up, or the adverse event is otherwise explained or not considered clinically significant by the Investigator. Adverse events not resolved by Day 90 will be considered ongoing.

Adverse events assessments will include photosensitivity assessment. Because safety data from IV SnPP administration at doses up to 3 mg/kg has shown photosensitivity in subjects exposed to sunlight or ultraviolet-A light following dosing [[Anderson 1986](#), [Berglund 1990](#), [Dover 1993](#), [Galbraith 1989](#), [Kappas 1988](#)], subjects will be advised to do the following for 30 days following treatment administration:

- Wear a broad-spectrum sunscreen that is at least SPF (sun protection factor) 30, even on cloudy or cool days. Sunscreen should be applied 30 minutes before going outside, giving the skin time to absorb it. Because sunscreen tends to be broken down over time by the sun and rubbed or washed off with sweating and water exposure, it should be reapplied at least every 2 hours outdoors and immediately after swimming or heavy sweating. At least 1 ounce (2 tablespoons) is needed to cover the entire body surface.
- Avoid direct sunlight, especially during the times of day when sun rays are strongest; sit in the shade.
- Avoid tanning beds.
- Wear long sleeves, pants, or long skirts when in the sun.
- Wear a hat with a wide brim all the way around to shade the face, ears, and neck.

- Wear sunglasses.

10.1 Investigator Reporting Requirements

The Investigator must immediately report (within 24 hours by a written report sent by fax or e-mail) all serious adverse events to the Sponsor, regardless of whether the Investigator believes that they are drug-related, including those events listed in the protocol as anticipated to occur in the study population independent of drug exposure (see Section 10.2).

These serious adverse events must be reported to:

[name], FASN, FNKF, FCRS
Medical Monitor
Renibus Therapeutics, Inc.

E-mail: [contact]
Fax: [[name]]([contact])

Because the Investigator is knowledgeable about the human subject (eg, medical history, concomitant medications), administers the study drug, monitors the subject's response to the study drug, is aware of the subject's clinical state and thus may be sensitive to distinctions between events due to an underlying disease process versus events that may be drug-related, and may have observed the event, the Investigator must include an assessment of causality (ie, whether there is a reasonable possibility that the study drug caused the event) in the report to the Sponsor. Copies of each report to the Sponsor will be kept in the Investigator's study file.

The Investigator is responsible for complying with their IRB/IEC's requirements for reporting serious adverse events. Any expedited safety report (ie, serious unexpected suspected adverse reaction) received from the Sponsor should be submitted to the IRB/IEC. Copies of each report and documentation of IRB/IEC notification will be kept in the investigator's study file.

The Investigator must record non-serious adverse events in the eCRF and report them to the Sponsor according to the timetable for reporting (eg, end of study).

Definitions:

Adverse Event: Adverse event means any untoward medical occurrence associated with the use of a drug in humans, whether or not considered drug related. An adverse event can be any unfavorable and unintended sign (eg, an abnormal laboratory finding), symptom, or disease temporally associated with the use of a drug, without any judgment about causality.

Adverse Reaction: Adverse reaction means any adverse event definitely caused by the drug.

Suspected Adverse Reaction: Suspected adverse reaction means any adverse event for which there is a "reasonable possibility" (ie, evidence indefinite but suggests a causal relationship between the drug and the adverse event) that the drug caused the adverse

event. By definition, a suspected adverse reaction is identical to the definition of adverse drug reaction per ICH E2A.

Examples that would suggest a causal relationship:

- A single occurrence of an event that is uncommon and known to be strongly associated with drug exposure (eg, angioedema, hepatic injury, Stevens-Johnson Syndrome)
- One or more occurrences of an event that is not commonly associated with drug exposure, but is otherwise uncommon in the population exposed to the drug (eg, tendon rupture)
- An aggregate analysis of specific events observed in a clinical study (eg, known consequences of the underlying disease or condition under investigation or other events that commonly occur in the study population independent of drug therapy) that indicates those events occur more frequently in the drug treatment group than in a concurrent or historical control group.

Unexpected Adverse Event or Unexpected Adverse Reaction: An adverse event or adverse reaction is considered “unexpected” if it is not listed in the Investigator’s Brochure or is not listed at the specificity or severity that has been observed.

Adverse events or adverse reactions that are mentioned as occurring with a class of drugs or as anticipated from the pharmacological properties of the drug will be considered “unexpected” if they are not specifically mentioned as occurring with the particular drug under investigation.

Until the Investigator’s Brochure is updated to include a new serious suspected adverse reaction, subsequent occurrences of similar serious suspected adverse reactions must be submitted expeditiously to FDA in Investigational New Drug (IND) Safety Reports and to other appropriate regulatory authorities in countries other than the United States in an Individual Case Safety Report or using a Council for International Organizations of Medical Sciences I form, as appropriate.

Serious Adverse Event or Serious Adverse Reaction: An adverse event or adverse reaction is considered “serious” if, in the view of either the Investigator or Sponsor, it results in any of the following outcomes:

- Death.
- A life-threatening adverse event.
- Inpatient hospitalization or prolongation of existing hospitalization.
- A persistent or significant incapacity or substantial disruption of the ability to conduct normal life functions.
- A congenital anomaly/birth defect.

Important medical events that may not result in death, be life-threatening, or require hospitalization may be considered serious when, based upon appropriate medical judgment, they may jeopardize the subject and may require medical or surgical intervention to prevent one of the outcomes listed in this definition.

If either the Investigator or Sponsor believes that the event is serious, it must be evaluated by the Sponsor for expedited reporting to regulatory authorities.

Life-Threatening Adverse Event or Life-Threatening Adverse Reaction: An adverse event or suspected adverse reaction is considered “life-threatening” if, in the view of either the Investigator or the Sponsor, its occurrence places the subject at immediate risk of death.

Serious Unexpected Suspected Adverse Reaction: An adverse event for which there is a reasonable possibility that the drug caused the adverse event, and it is not listed in the Investigator’s Brochure or is not listed at the specificity or severity that has been observed, and it results in any of the serious outcomes listed above. This criterion is consistent with the concepts of FDA 21 Code of Federal Regulation (CFR) 312 and the ICH E2A Guideline for expedited safety reports.

The Sponsor must notify the appropriate regulatory authority(ies) and all participating Investigators in an expedited safety report (eg, IND Safety Report or Individual Case Safety Report) of potentially serious risks from clinical studies or any other source (ie, a serious unexpected suspected adverse reaction), as soon as possible, but no later than 15 calendar days after the Sponsor receives the safety information and determines that the information qualifies for reporting.

During the course of drug development, the Sponsor may become aware of new safety information from a variety of sources and will decide if an individual case of a serious and unexpected adverse event meets the criteria for reporting to regulatory authorities.

If the adverse event does not meet all criteria (ie, reasonable possibility of causality, serious and unexpected), it should not be submitted as an expedited safety report.

Any unexpected fatal or life-threatening suspected adverse reaction must be reported to regulatory authorities no later than 7 calendar days after the Sponsor receives the safety information.

10.2 Assessment of Relationship to Study Drug

The following criteria must be used to by the Investigator to characterize the relationship or association of study drug in causing or contributing to the adverse event:

Unrelated: Relationship suggests no association of the event to study drug; the event is related to other etiologies, such as the subject’s clinical state or concomitant medications

Unlikely: Relationship suggests an unlikely association of the event to study drug given the subject’s current disease state

Possible: Relationship suggests treatment with study drug caused or contributed to the event; the event follows a reasonable temporal sequence from administration of study drug and/or follows a known response pattern to the study drug; the event might have been produced by other factors (eg, the subject’s clinical state or other modes of therapy administered to the subject)

Related: Relationship suggests a definite causal relationship to study drug; the event follows a known response pattern to the study drug and cannot be reasonably explained by the known characteristics of the subject's clinical state or other modes of therapy administered to the subject

10.3 Assessment of Severity

The following criteria must be used by the Investigator to rate the intensity of the adverse event:

Mild: Awareness of signs or symptoms, but easily tolerated and are of minor irritant type causing no loss of time from normal activities; symptoms do not require therapy or a medical evaluation; signs and symptoms are transient

Moderate: Events introduce a low level of inconvenience or concern to the subject and may interfere with daily activities, but are usually improved by simple therapeutic measures; moderate experiences may cause some interference with functioning

Severe: Events interrupt the subject's normal daily activities and generally require systemic drug therapy or other treatment; they are usually incapacitating

10.4 Breaking the Blind

This is a double-blind study. Breaking the blind in a clinical trial on an emergency basis should only occur when knowledge of the treatment to which a subject was allocated would have implications for the emergency medical management of the subject or if required for regulatory reporting. If necessary, emergency breaking of the blind can be conducted through the Interactive Web Response System by the Medical Monitor. The reason for unblinding, person conducting the unblinding, person(s) who know the unblinded treatment, and date/time of unblinding will be recorded.

11 STATISTICAL CONSIDERATIONS

This section outlines the statistical considerations to be used in the analysis of data from the study. A separate SAP will describe data handling and statistical techniques.

11.1 Criteria for Evaluation

Efficacy assessments include the following:

- Change in preconditioning plasma biomarkers from Baseline (pre-dose) through Day 1 pre-op:
 - HO-1, ferritin, and IL-10
- Change in renal tubular injury biomarkers post-cardiac surgery through Day 3:
 - KIM-1, cystatin C, and NGAL

- Reduction in urine output (documented oliguria of <0.5 mL/kg/hour, not due to urinary tract obstruction) for more than 6 hours post-cardiac surgery through Day 3.
- Incidence of AKI post-cardiac surgery through Day 5, defined as:
 - An absolute increase in serum creatinine by 0.5 mg/dL, which is present over 2 laboratory measurements at least 12 hours apart; or
 - An increase in serum creatinine $\geq 1.5X$ Baseline.
- Severity of AKI post-cardiac surgery through Day 7.
- Average increase in serum creatinine post-cardiac surgery through Day 7 or until Discharge if prior to Day 7.
- Occurrence of MAKE30 and MAKE90 post-cardiac surgery.
- Proportion of subjects experiencing MAKE30.
- Proportion of subjects experiencing MAKE90.
- Days on ventilator.
- Days in intensive care unit.
- Hospital length of stay.
- Readmission rate.
- Changes in biomarkers of RBT-1 activity and/or kidney function.

Safety assessments include the following:

- Adverse events.
- Laboratory data and vital signs at regular intervals.

11.2 Study Populations

The efficacy analyses will be conducted using the Intent-to-Treat population (all randomized subjects) and Per Protocol population (all randomized subjects who had no major protocol deviations). Safety analyses will be conducted using all subjects receiving any amount of study drug.

11.3 Data Analysis

Details of the efficacy analysis and safety analysis will be defined in the SAP. When appropriate, summary statistics will be provided (number of non-missing values, mean, median, standard deviation, minimum, and maximum for continuous variables and number and percentage of subjects for categorical variables) by treatment group for all measures, including demographic and baseline assessments, safety, and efficacy endpoints. Baseline for all safety and efficacy endpoints is defined as the last observations before administration of study drug.

11.4 Sample Size Calculations

Assuming an increase of 30% in the primary biomarkers from baseline in the RBT-1 treated groups versus a 10% reduction in the placebo group and a standard deviation of 10%, 6 subjects per group would provide 80% power to detect a difference between treatment and placebo groups with a significance level of 0.05. From a safety perspective, 40 subjects per group is consistent with the sample size typically used in early-stage clinical trials.

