Statistics: Details of the efficacy analysis and safety analysis will be defined in the statistical analysis plan (SAP).

Analysis Populations: The efficacy analyses will be conducted using the Intent-to-Treat population (all randomized subjects) and Per Protocol population (all randomized subjects who had no major protocol deviations). Safety analyses will be conducted using all subjects receiving any amount of study drug.

Data Analysis: When appropriate, summary statistics will be provided (number of non-missing values, mean, median, standard deviation, minimum, and maximum for continuous variables and number and percentage of subjects for categorical variables) by treatment group for all measures, including demographic and baseline assessments, safety, and efficacy endpoints. Baseline for all safety and efficacy endpoints is defined as the last observations before administration of study drug.

Sample Size Estimate: Assuming an increase of 30% in the primary biomarkers from baseline in the RBT-1 treated groups versus a 10% reduction in the placebo group and a standard deviation of 10%, 6 subjects per group would provide 80% power to detect a difference between treatment and placebo groups with a significance level of 0.05. From a safety perspective, 40 subjects per group is consistent with the sample size typically used in early-stage clinical trials.

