## 1 INTRODUCTION

The purpose of this statistical analysis plan (SAP) is to present the statistical methodology that will be used for the interim and final analyses of Renibus Therapeutics, Inc. protocol REN-004. This plan also provides a description of the tables, figures, and listings that will be included in the final statistical report. It is based on the protocol version 5 dated 25 August 2022 and on the annotated electronic case report form (eCRF). In case of differences in terms of descriptions or explanations between the SAP and the clinical protocol, the SAP will supersede the protocol. Any deviation to this SAP would be reported in the clinical study report (CSR).

[figure not shown]

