## 5 EFFICACY ENDPOINTS

### 5.1 Primary Efficacy Endpoint

The primary efficacy composite endpoint is defined as the geometric mean of the ratios of the maximum PreOp value (Visit 1b or Day 1 PreOp) over Baseline (Visit 1a) for the 3 preconditioning biomarkers,

$$Exp \left\{ \frac{1}{3} \cdot \left[ Log \left( \frac{\text{max PreOp HO-1}}{\text{Baseline HO-1}} \right) + Log \left( \frac{\text{max PreOp Ferritin}}{\text{Baseline Ferritin}} \right) + Log \left( \frac{\text{max PreOp IL-10}}{\text{Baseline IL-10}} \right) \right] \right\}.$$

For sensitivity analysis, this composite endpoint will also be defined as the geometric mean of the ratios of average of Day 1 PostOp through Day 3 over baseline for the 3 preconditioning biomarkers {HO-1, Ferritin, and IL-10}, where Avg (average) is calculated as the area under the biomarker-time curve (AUC) divided by the duration in the AUC calculation (AUC/D), and

$$AUC = \left\{ \sum_{i=2}^n (v_i + v_{(i-1)}) (t_i - t_{(i-1)}) \right\} / 2,$$

$$D = t_n - t_1$$

$v_1$  and  $v_n$  are the first (Visit 1b or Day 1 for subjects dosed 36 to 48 hours or 24 to <36 hours prior to surgery, respectively) and last (Study Day 3) biomarker values after study drug administration,  $t_i$  is the date and time of the  $i^{\text{th}}$  biomarker test.

Baseline for this composite endpoint is calculated as

$$(\text{Baseline HO-1} * \text{Baseline ferritin} * \text{Baseline IL-10})^{1/3}.$$

Because an increase in plasma biomarkers is beneficial and because the ratios are calculated as the follow-up value over the baseline value, a value >1 for the primary efficacy endpoint would indicate benefit.

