## 7 STATISTICAL METHODOLOGY

### 7.1 Determination of Sample Size

There will be three treatment groups; the two active (high dose [HD] 90/240 and low dose [LD] 45/240) groups will be compared to the control group. Using gatekeeping procedure for multiple comparisons and assuming the primary endpoint log composite score derived from this study is comparable to the score derived from the REN-003 and REN-001A studies (HD: mean  $\pm$  SD 1.30 $\pm$ 0.56, LD: 1.07 $\pm$ 0.52, and placebo: 0.19 $\pm$ 0.19), a sample size of 10 subjects per group will provide >80% power for the between group comparisons with two-sided  $\alpha=0.05$  significance level.

Using the REN-003 Study “FDA Safety Summary-1 Updated Feb2020.docx” non-surgical healthy volunteer and CKD patient data mixture, the secondary endpoint log composite score is estimated as 0.41  $\pm$  0.51. Thus, with the sample size of 10, 20, and 30 subjects per group, the study will have 40%, 69%, and 86% power, respectively, to detect a between active group and placebo group difference in the mean log composite score of 0.4, or a between group ratio of 1.5 in the composite score.

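### The protocol's power statement does not follow from its own inputs: 6 per group gives over 99.9% power, not 80%, and SAP 7.1 plans on different assumptions

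*Protocol*

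**What the plan says.** Protocol 11.4 sets out the effect as "Assuming an increase of 30% in the primary biomarkers from baseline in the RBT-1 treated groups" "versus a 10% reduction in the placebo group", takes a standard deviation of 10%, and states that "6 subjects per group would provide 80% power to detect a difference between treatment and placebo groups with a significance level of 0.05". The Sample Size Estimate in the synopsis (Protocol section 4) repeats this. Neither place names the test or says whether the 0.05 is one-sided or two-sided.

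Planned enrolment is 126 subjects, 42 per group. The only support given for a number of that order is a separate sentence: "From a safety perspective, 40 subjects per group is consistent with the sample size typically used in early-stage clinical trials".

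SAP 7.1 gives a different calculation for the primary endpoint. It takes log composite scores from studies REN-003 and REN-001A, with means (SD) of 1.30 (0.56) for high dose, 1.07 (0.52) for low dose and 0.19 (0.19) for placebo. It concludes that "a sample size of 10 subjects per group will provide >80% power for the between group comparisons" at two-sided 0.05. By SAP 5.1 the composite is the geometric mean, over HO-1, ferritin and IL-10, of the ratio of the highest pre-operative value to baseline.

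SAP section 1 sets the order of precedence: "In case of differences in terms of descriptions or explanations between the SAP and the clinical protocol, the SAP will supersede the protocol".

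**The concern.** A 40-point separation with a standard deviation of 10 points is a very large effect. Six subjects per group should detect it almost every time, so a figure of 80% suggests that the power or one of the inputs was misstated. This is the protocol's only power statement for its primary objective, it appears twice, and a reader cannot reproduce it.

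The protocol and the SAP also appear to expect different things of the same three biomarkers, including the direction of change on placebo. If so, the two documents do not share one set of planning assumptions, and a reader of the protocol alone gets the wrong picture of the expected effect and its variability.

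**Working it through.** **1. The protocol's figure**

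Inputs from Protocol 11.4: change of +30% on RBT-1 and −10% on placebo, SD 10%, alpha 0.05, n = 6 per group. I take a two-sided two-sample t test, in line with the SAP's two-sided convention in section 7.2.

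- Difference: 30 − (−10) = 40 points.
- Standardised difference: d = 40/10 = 4.0.
- Noncentrality: d × √(n/2) = 4.0 × √3 = 6.93, with 2n − 2 = 10 degrees of freedom and critical value 2.228.
- Power from the noncentral t distribution: 99.999%.

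| n per group | Power at d = 4.0 |
|---|---|
| 2 | 56.5% |
| 3 | 94.8% |
| 4 | 99.6% |
| 5 | 99.98% |
| 6 | 99.999% |

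The stated 80% is not reproduced.

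**2. What would give 80% at 6 per group**

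Solving for d gives 1.80. With a 40-point difference that needs an SD of 40/1.796 = 22.3%. With an SD of 10% it needs a difference of about 18 points.

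**3. Other readings of the same inputs (n = 6)**

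| Reading | Power |
|---|---|
| One-sided 0.05 | 99.9999% |
| Normal approximation, two-sided 0.05 | 99.99997% |
| Two-sided 0.025 | 99.99% |
| Two-sided 0.05/6 | 99.85% |
| Two-sided 0.001 | 95.5% |
| All three biomarkers significant (independence assumed) | 99.996% |
| Log scale, ln(1.30/0.90) = 0.368, SD 0.10 | 99.99% |
| SD inflated by √2 | 99.2% |
| Exact Mann-Whitney, 4,000 simulations | about 100% |

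None comes near 80%. If the placebo change were meant as +10% (my assumption; d = 20/10 = 2.0), n = 5 gives 79.1% and n = 6 gives 87.6%, which is still not 80%.

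**4. Comparison with SAP 7.1**

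The scales differ, so I put both on the ratio-to-baseline scale. The protocol column is my conversion; the protocol states no log values.

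| | Protocol 11.4 | SAP 7.1 |
|---|---|---|
| Active, ratio to baseline | 1.30 | exp(1.30) = 3.67 high dose; exp(1.07) = 2.92 low dose |
| Placebo, ratio to baseline | 0.90 | exp(0.19) = 1.21 |
| Active/placebo ratio | 1.30/0.90 = 1.44 | exp(1.11) = 3.03; exp(0.88) = 2.41 |
| SD, log scale | about 10/130 = 0.08 active, 10/90 = 0.11 placebo | 0.56 and 0.52 active, 0.19 placebo |
| n per group | 6 | 10 |
| Stated power | 80% | over 80% |

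**5. Does the SAP's own figure hold?**

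Yes. Because the SAP's SDs are unequal, I simulated the Welch test.

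| n per group | High dose | Low dose |
|---|---|---|
| 6 | 96% | 90% |
| 10 | 99.96% | 99.5% |
| 20 | over 99.9% | over 99.9% |

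A pooled-variance t test gives 99.99% and 99.7% at 10 per group. The SAP's claim of more than 80% is true, with a wide margin.

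**6. Are the two bases interchangeable?**

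As a sensitivity check only, I combined the protocol's ratio of 1.44 (log difference 0.368) with the SAP's SDs, a pairing that neither document proposes. Welch power is 26–29% at 6 per group and 97–98% at 40 per group. The bases cannot be swapped at 6 per group, but enrolment at the planned level is adequate even under this pairing.

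**The case against.** The strongest reply is that nothing in the trial depends on this sentence. Enrolment is 42 per group, the protocol leaves analysis details to the SAP, SAP 7.1 has its own calculation tied to the actual primary endpoint, and the SAP takes precedence. This stands, and it limits the point to a correction of the text. It does not make the sentence true on its own inputs. The SAP also states that it is based on the protocol version dated 25 August 2022, the date on this synopsis, so the sentence is current text.

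A second reply is that 80% is loose wording for at least 80%, much as the SAP writes over 80% where its inputs give over 99%. The SAP's wording is a true inequality; the protocol's is not written as one. Read generously it would be true, but 3 per group would already meet it, so it would not explain 6.

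A third is that the protocol and SAP describe different quantities: percentage change in biomarkers against a log composite of maxima. Taking the larger of two pre-operative values also pushes the ratio upward in any arm, placebo included. That is a fair caution against reading the converted figures as exact, and it may explain part of the gap on placebo. The inputs and sample sizes still differ, and the protocol does not mention the SAP's basis.

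Finally, simply changing 80% to over 99.9% could entrench a mistyped input, since an SD of about 22% would reproduce 80%. That objection is sound and is why replacement is the better remedy.

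**Conclusion.** The concern holds. On the stated inputs, 6 per group gives over 99.9% power at 0.05, one-sided or two-sided, by t test or normal approximation. The stated 80% belongs to a standardised difference of 1.80, less than half the 4.0 that the protocol assumes. The documents do not show which number is wrong.

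The inputs also differ from those in SAP 7.1 in scale, effect size, variability, direction of the placebo change and n. The size of that gap (ratio 1.44 against 3.03 or 2.41) rests on my conversion to a common scale.

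The practical effect is small. The error understates power on the protocol's own inputs, and the sample size rests on safety. This is a correction that should be made, not a shortfall in sample size.

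**What to change.** **Preferred.** In Protocol 11.4 and the synopsis, replace the power sentence with the SAP 7.1 basis, for example:

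> Assuming log composite means (SD) of 1.30 (0.56) for high dose, 1.07 (0.52) for low dose and 0.19 (0.19) for placebo, 10 subjects per group give over 99% power for each dose versus placebo at two-sided 0.05.

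**Alternative.** If the percentage-change basis is kept, first verify the difference, the SD, the test and its sidedness against the original calculation. Then state the power they give. If the printed inputs are confirmed, that is over 99.9% at 6 per group.

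Either way, keep the safety sentence as the reason for about 40 per group. Power for the secondary composite at 40 per group (about 93% for a log difference of 0.4 with SD 0.51, the SAP 7.1 inputs) may be added for information, but not as the reason for the sample size.

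The cost is one sentence in two places, with no change to enrolment, analysis or alpha.
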